#### **10.4 Tissue Banking**

All research specimens are shipped to the study repository at the UTMDACC for storage which will be housed in the laboratory of the Principal Investigator, [name]. The laboratory is equipped with five -80 degree freezers which serve as repositories for research samples.

Biologic specimens collected during the conduct of each clinical trial that are not used during the course of the study will be considered deliverables under the contract and thus the property of the NCI. At study completion, NCI reserves the option to either retain or relinquish ownership of the unused biologic specimens. If NCI retains ownership of specimens, the Contractor shall collect, verify and transfer the requested biologic specimens from the site to a NCI-specified repository or laboratory at NCI's expense.

### **11. REPORTING ADVERSE EVENTS**

DEFINITION: AE means any untoward medical occurrence associated with the use of a drug in humans, whether or not considered drug related. An AE can therefore be any unfavorable and unintended sign), symptom, or disease temporally associated with participation in a study, whether or not related to that participation. This includes all deaths that occur while a participant is on a study.

Please note that all abnormal clinical laboratory values that are determined to be of clinical significance based on a physician's assessment are to be reported as AEs. Those labs determined to be of no clinical significance or of unknown clinical significance (per the physician's assessment) should not be reported as AEs. Any lab value of unknown clinical significance should continue to be investigated/followed-up further for a final determination, if possible.

A list of AEs that have occurred or might occur can be found in §6.2 Reported Adverse Events and Potential Risks, as well as the Investigator Brochure or package insert.

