### 6.2 Reported Adverse Events and Potential Risks

Aspirin has been associated with gastrointestinal (GI) side effects. GI side effects include stomach pain, heartburn, nausea, vomiting, and gross GI bleeding. Minor upper GI symptoms, such as dyspepsia, are common and can occur anytime during therapy. Aspirin has also been associated with an increased risk of hemorrhagic stroke. Aspirin has also been associated with elevated hepatic enzymes, blood urea nitrogen and serum creatinine, hyperkalemia, proteinuria, and prolonged bleeding time. High-dose aspirin has been associated with tinnitus.

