## 7. CLINICAL EVALUATIONS AND PROCEDURES

### 7.1 Schedule of Events

#### SCHEDULE OF EVENTS

Evaluation/ Procedure	Screening	Baseline Visit/ Eligibility Verification	Randomization (within 45 days of qualifying endoscopy) b	Month 1 (+/- 7 days) Phone contact	Months 3,6,9 (+7 days) and Month 15 (+/- 14 days) Phone or mail contact	Month 12 (+/- 30 days) EGD with biopsies. End of treatment	Month 18 (+/- 30 days) EGD with biopsies. Study termination
Informed Consent		X					
Assess Eligibility	X	X					
Baseline History Assessment	X	X a					
Symptom Assessment Questionnaire	X						
Symptom Assessment		X	X	X	X	X	X
Physical Exam		X				X	X
Vital Signs/ Height and Weight c		X				X	X
Laboratory Tests		X				X	
Pregnancy Test d		X	X				
Qualifying EGD with Biopsies		X g				X h	X h
Biomarkers		X				X	X
Concomitant Medications	X	X	X	X	X	X	X
Dispense Study Agent			X In person or by mail		X Mail e		
Collect Study Agent					X i	X	
Review Pill Diary/Record			X	X	X	X	
Adverse Events			X	X	X	X	X
Telephone Contact	X		X b	X	X		
Interval questionnaire					X	X	
Your Health and Well-Being (SF-36) survey		X				X	

a Do not repeat the Baseline History Assessment Questionnaire at Baseline. If participant is registered to study, enter Baseline History Assessment Questionnaire captured at Screening.

b In person or by phone.

c Do not repeat height measurement after Baseline Testing.

d In persons of childbearing potential a serum pregnancy test must be done at the baseline visit. If positive at that baseline visit that participant is a screen failure. Randomization may occur within 21 days from the baseline visit negative pregnancy test without repeating the test. For randomization to occur after this 21 day window from the baseline visit negative pregnancy test date a repeat pregnancy test must be done and must be known to be negative prior to randomization and medication dispensing.

e Study medication is distributed after randomization and at 3, 6, and 9 months only.

f Study medication is collected at 3, 6, 9 and 12 months.

g Qualifying endoscopy.

h A clinically indicated surveillance endoscopy.

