### 8.2 Secondary Endpoints

- 8.2.1 Safety will be assessed by comparison of adverse events using the NCI Common Terminology Criteria for Adverse Events (CTCAE) version 4.0. AEs will be assessed according to the CTCAE grade associated with the AE term. AEs that do not have a corresponding CTCAE term will be assessed according to the general guidelines for grading used in the CTCAE v4.0. as stated in Section 11.1.3.1. We will closely monitor the toxicity profile and tolerability in each group. Safety will be assessed by monitoring routine clinical parameters at baseline and at each visit throughout the trial (including Month 1, every 3 months by phone calls and/or mail interviews and in person at 12 and 18 months), and by monitoring laboratory parameters at baseline and at 12 months. All AEs will be recorded and graded during clinical visits, whether or not they are considered drug-related. All participants will be monitored for toxicity from the time of randomization. Each treatment arm will be monitored separately for severe toxicities (grade 3 and 4 and SAEs). We will be especially vigilant about the incidence of gastrointestinal (gastric and duodenal ulcers, gastritis, gastrointestinal bleeding or perforation, hematemesis) and hematological (anemia, thrombocytopenia) events. Toxicity will be considered drug-related based on clinical assessment. In addition, at the completion of the study, the frequency of toxicities will be compared between the placebo and aspirin groups.

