### 13.5 Secondary Objectives, Endpoints, Analysis Plans

#### Secondary Endpoints

**Safety will be assessed by comparison of adverse events using the NCI Common Terminology Criteria for Adverse Events (CTCAE) version 4.0** (Refer to Section 8.2.1). Safety will be assessed by monitoring routine clinical parameters at baseline and at each visit throughout the trial (including every 3 months by phone calls and/or mail interviews and in person at 12 and 18 months), and by monitoring laboratory parameters at baseline and at 12 months. All AEs will be recorded and graded during clinical visits, whether or not they are considered drug-related. All participants will be monitored for toxicity from the time of randomization. Each treatment arm will be monitored separately for severe toxicities (grade 3 and 4 and SAEs). We will be especially vigilant about the incidence of gastrointestinal (gastric and duodenal ulcers, gastritis, gastrointestinal bleeding or perforation, hematemesis) and hematological (anemia, thrombocytopenia) events. Toxicity will be considered drug-related based on clinical assessment. In addition, at the completion of the study, the frequency of toxicities will be compared between the placebo and aspirin groups.

**The SF-36 is a multi-purpose, short-form health survey with 36 questions. It yields an 8-scale profile of functional health and well-being scores as well as psychometrically-based physical and mental health summary measures and a preference-based health utility index.** It is a generic

measure, as opposed to one that targets a specific age, disease, or treatment group. Since a secondary endpoint of our study is to determine safety in a specific clinical setting (use of aspirin following radiofrequency ablation, we will compare measures of health and well-being between those receiving aspirin and those receiving placebo. Bivariate analyses will be performed on study entry and completion of the on-drug period. Multivariate analyses will be performed between groups after controlling for potential confounders.

**Differences in the change of CDX2 mRNA levels from baseline to 18 months post-randomization** in esophageal squamous tissue between participants taking aspirin supplementation versus those taking placebo.

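### No by-arm analysis of the laboratory values is planned, and the adverse-event rule filters them by physician judgment, so the safety comparison can miss or dilute laboratory toxicity that the baseline and Month 12 panels would show

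*Combined protocol and SAP*

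**What the plan says.** All references are to the combined protocol and SAP.

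- **What becomes an adverse event.** Section 11 states that "all abnormal clinical laboratory values that are determined to be of clinical significance based on a physician's assessment are to be reported as AEs". Results judged to be of no significance, "or of unknown clinical significance (per the physician's assessment) should not be reported as AEs". The next sentence adds: "Any lab value of unknown clinical significance should continue to be investigated/followed-up further for a final determination, if possible". Section 11.1.5 applies the same opinion test to the laboratory abnormalities that are followed as adverse events.
- **What is compared.** Section 8.2.1 opens with "Safety will be assessed by comparison of adverse events using the NCI Common Terminology Criteria for Adverse Events (CTCAE) version 4.0" and says that at study completion "the frequency of toxicities will be compared between the placebo and aspirin groups". Section 13.5 repeats both. Anemia and thrombocytopenia are among the events singled out for special vigilance. The other between-arm safety comparison in these sections is the SF-36 health survey.
- **What is measured.** Both sections also say safety is assessed "by monitoring laboratory parameters at baseline and at 12 months". Sections 7.2.2 and 7.4 list the same panel at both times: blood count with differential, creatinine, electrolytes including sodium and potassium, AST, ALT and total bilirubin. In the Schedule of Events the laboratory row is marked at Baseline and Month 12 only, and section 7.5 lists no laboratory test at Month 18.
- **What is expected of the agent.** Section 6.2 associates aspirin with "elevated hepatic enzymes, blood urea nitrogen and serum creatinine, hyperkalemia, proteinuria, and prolonged bleeding time".

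**The concern.** Changes in hemoglobin, platelets, creatinine, potassium or transaminases often cause no symptoms, so the blood panel is the main way to see them. Under section 11 such a change reaches the adverse-event data only if a physician calls it clinically significant. That judgment is made at several sites with no common threshold. Because toxicity is compared between arms through adverse events and nothing else is planned for the laboratory values, a shift judged not significant, or never resolved, drops out of the comparison even if the measured value would meet a CTCAE grade.

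At stake is how well the trial can answer the safety part of its aim. Section 1.1 places safety in the primary objective, although section 8.2.1 lists it as a secondary endpoint. The primary CDX2 test is not affected.

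**Working it through.** The plan states no figure on this point, so the check sets the sections against each other.

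**1. Can a gradable laboratory change be left out of the adverse-event data?** Yes. Section 11 makes physician judgment the only test and names no grade at which reporting becomes mandatory. Sections 8.2.1 and 11.1.3 attach CTCAE grades to adverse events; no section says that every laboratory value is graded. A value left out under section 11 is therefore not graded by another route.

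**2. Is there another analysis that would pick it up?** None is specified. Sections 8.2.1 and 13.5 mention monitoring of laboratory parameters but give no shift table, grade summary, mean change or test. Section 13.4 plans t-tests and Wilcoxon tests for the primary and secondary endpoints in general terms and names no laboratory variable. Monitoring of Grade 3 and 4 toxicities by arm does not fill the gap, because it too works on events that have been reported and graded.

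**3. Does follow-up of unknown results close the gap?** Only in part. Month 12 is the only scheduled panel after baseline. Participants are contacted at Month 15 and examined at Month 18, with adverse events assessed both times, but blood is not scheduled to be drawn. Resolving an unknown Month 12 value depends on an unscheduled test, and the plan asks for that only if possible. Results judged to be of no significance are not covered by the follow-up sentence.

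**4. Which named risks are affected?** Section 6.2 lists six laboratory-type risks. Three are measured by the panel: hepatic enzymes (AST, ALT), creatinine and potassium. Three are not in it: blood urea nitrogen, proteinuria and bleeding time. Hemoglobin and platelets, which bear on the anemia and thrombocytopenia singled out in section 8.2.1, are in the panel.

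**5. Direction of the effect.** Let pA and pP be the true proportions with a laboratory abnormality on aspirin and placebo, and c the share of abnormalities that physicians report. If c is the same in both arms, the expected proportions seen are c × pA and c × pP. Then:

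- difference seen = c × (pA − pP);
- ratio seen = (c × pA) / (c × pP) = pA / pP, unchanged for c > 0.

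The difference shrinks in proportion to c, while the expected ratio does not move. Equal c is an assumption. It is supported by section 6.9, which blinds participants and all investigators other than the statistician and the site pharmacist.

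**6. Size.** The documents give no value for pA, pP or c. The possible range runs from no loss (c = 1) to complete loss (c = 0), and nothing in the plan narrows it.

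**7. Why change from baseline is needed.** Section 4.1.7 admits participants with abnormal baseline values, for example hemoglobin down to 10 g/dL, AST and ALT up to 2.5 times the upper limit of normal, and bilirubin up to twice that limit. A Month 12 grade alone would mix existing abnormality with change on treatment.

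**The case against.** The strongest reply is that section 11 is a clear and internally consistent rule. Clinically significant anemia, thrombocytopenia, creatinine and transaminase changes remain reportable. Unknown results are to be pursued, and participants stay on study for six months after Month 12. Laboratory monitoring is named as a safety element in its own right. Assessors are blinded, and with about 20 participants per arm even a full count of laboratory shifts would give an imprecise comparison.

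Most of this stands, and it rules out several stronger readings that a reader might infer:

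- **That an unknown Month 12 result never becomes an adverse event.** The follow-up sentence allows it to, although no test is scheduled for the purpose.
- **That laboratory toxicity is under-counted.** The documents show only that it can be, since they give no rates and no reporting share.
- **That graded values are already collected.** Values that can be graded are measured, but the plan assigns grades to adverse events only.
- **That the rule favors aspirin.** Blinding makes loss of signal the expected result, together with variation between sites.
- **That the safety conclusion would rest mainly on symptoms.** Significant laboratory results, physical examinations and endoscopies at 12 and 18 months also contribute.
- **That section 11 contradicts the Grade 1 description in section 11.1.3**, which includes purely diagnostic observations. That scale grades events already classed as adverse events; it does not decide which laboratory results become events.

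The reply does not supply the missing analysis. Monitoring laboratory parameters is not a specified between-arm summary. Limited precision is a reason to report mean change with confidence intervals as well as counts, not a reason to leave the values unanalyzed.

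**Conclusion.** The point holds as a gap in the safety analysis. An opinion-based filter with no grade floor decides which laboratory changes enter the adverse-event data, toxicity is compared between arms only through those data, and no analysis of the measured values is planned. The comparison can miss or dilute changes in laboratory measures that the protocol itself names as risks of the agent or ties to watched events.

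The size is unknown and cannot be computed from the documents. The conclusion that signal is lost, without bias toward an arm, assumes that reporting is about equal in the two arms. Blinding supports this but does not guarantee it; for instance, reporting could still differ if abnormalities in one arm were more severe. The improvement is inexpensive and worth making because safety is part of the stated primary objective.

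**What to change.** Add to sections 8.2.1 and 13.5:

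*For hemoglobin, leukocytes, neutrophils, platelets, creatinine, sodium, potassium, AST, ALT and total bilirubin, CTCAE v4.0 grades will be assigned, where criteria exist, from the measured baseline and Month 12 values, whether or not an adverse event was reported. Grade shift and mean change from baseline to Month 12 will be tabulated by arm with 95% confidence intervals, separately from clinician-judged adverse events. Values whose clinical significance remains undetermined will be listed by arm.*

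The reporting rule in section 11 need not change, because the table does not depend on it.

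The cost is one programmed table and a listing. The blood draws are already scheduled. Laboratory values would have to be entered if they are not already in the study database, which the documents do not settle. A small drawback is that low-grade shifts of little clinical importance will appear in the table. Blood urea nitrogen, proteinuria and bleeding time are not measured under the plan, so this change does not cover them.

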## 11.1 Adverse Events

### 11.1.1 Reportable AEs

All AEs that occur after the informed consent is signed and baseline assessments are completed (including run-in) must be recorded on the AE CRF whether or not related to study agent.

### 11.1.2 AE Data Elements:

The following data elements are required for adverse event reporting.

- AE verbatim term
- CTCAE (MedDRA) System Organ Class (SOC)
- NCI Common Terminology Criteria for Adverse Events version 4.0 (CTCAE v4.0) AE term (MedDRA lowest level term)
- Event onset date and event ended date
- Treatment assignment code (TAC) at time of AE onset
- Severity grade
- Attribution to study agent (relatedness)
- Whether or not the event was reported as a serious adverse event (SAE)
- Whether or not the participant dropped due to the event
- Outcome of the event

### 11.1.3 Severity of AEs

11.1.3.1 Identify the AE using the CTCAE version 4.0. The CTCAE provides descriptive terminology (MedDRA lowest level term) and a grading scale for each AE listed. A copy of the CTCAE can be found at [http://ctep.cancer.gov/protocolDevelopment/electronic\\_applications/ctc.htm](http://ctep.cancer.gov/protocolDevelopment/electronic_applications/ctc.htm)

AEs will be assessed according to the grade associated with the CTCAE term. AEs that do not have a corresponding CTCAE term will be assessed according to the general guidelines for grading used in the CTCAE v4.0, as stated below.

#### CTCAE v4.0 general severity guidelines:

Grade	Severity	Description
1	Mild	Mild; asymptomatic or mild symptoms; clinical or diagnostic observations only; intervention not indicated.
2	Moderate	Moderate; minimal, local or noninvasive intervention indicated; limiting age-appropriate instrumental activities of daily living (ADL)*.

Grade	Severity	Description
3	Severe	Severe or medically significant but not immediately life-threatening; hospitalization or prolongation of hospitalization indicated; disabling; limiting self-care ADL**.
4	Life-threatening	Life-threatening consequences; urgent intervention indicated.
5	Fatal	Death related to AE.

## ADL

\*Instrumental ADL refers to preparing meals, shopping for groceries or clothes, using the telephone, managing money, *etc.*

\*\*Self-care ADL refers to bathing, dressing and undressing, feeding self, using the toilet, taking medications, and not bedridden.

### 11.1.4 Assessment of relationship of AE to treatment

The possibility that the adverse event is related to study agent will be classified as one of the following: not related, unlikely, possible, probable, definite.

### 11.1.5 Follow-up of AEs

All AEs, including lab abnormalities that in the opinion of the investigator are clinically significant, will be followed according to good medical practices and documented as such.

## 11.2 Serious Adverse Events

11.2.1 Regulations at 21 CFR §312.32 (revised April 1, 2014) defines an SAE as any untoward medical occurrence that at any dose has one or more of the following outcomes:

- Death
- A life-threatening AE
- Inpatient hospitalization or prolongation of existing hospitalization
- A persistent or significant incapacity or substantial disruption of the ability to perform normal life functions
- A congenital anomaly or birth defect
- Important medical events that may not be immediately life-threatening or result in death or hospitalization should also be considered serious when, based upon appropriate medical judgment, they may jeopardize the patient and may require intervention to prevent one of the other outcomes.

### 11.2.2 Reporting SAEs to DCP

The organization that experiences the serious adverse event (SAE) should report the SAE to the following 3 entities: 1) NCI DCP, 2) DCP's regulatory contractor CCSA, and 3) MDACC, the CLO. Detailed reporting instructions are provided below. In addition, all participating organizations will follow their IRB requirements for SAE reporting.

11.2.2.1 The Lead Organization and all Participating Organizations will report SAEs on the DCP SAE form found at <http://prevention.cancer.gov/clinical-trials/clinical-trials-management/protocol-information-office/pio-instructions-and-tools/2012-consortia>.

### **11.2.2.2 Reporting within 24 hours of knowledge of the event.**

#### **11.2.2.2(A) Report to the NCI DCP Medical Monitor within 24 hours:**

Contact the DCP Medical Monitor by phone within 24 hours of knowledge of the event.

[name], DO, MSc  
National Cancer Institute  
Division of Cancer Prevention  
Gastrointestinal and Other Cancers Research Group  
[name]  
Rockville, MD 20850  
[contact]  
Fax (with cover sheet, Attn: [name]): [contact]  
Email: [contact]  
[contact]

Include the following information when calling the Medical Monitor:

- Date and time of the SAE
- Date and time of the SAE report
- Name of reporter
- Call back phone number
- Affiliation/Institution conducting the study
- DCP protocol number
- Title of protocol
- Description of the SAE, including attribution to drug and expectedness

#### **11.2.2.2(B) Report to the Consortium Lead Organization (CLO) PI ([name]) within 24 hours of knowledge of the event:**

Report all SAEs to the Consortium Lead Organization PI ([name]) within 24 hours of knowledge of the event. The same information reported to the DCP Medical Monitor should be provided to the CLO Coordinator via email, phone or fax within 24 hours of knowledge of the event.

### **11.2.2.3 Reporting within 48 hours of knowledge of the event:**

11.2.2.3 (A) Email the written SAE reports to the DCP Medical Monitor within 48 hours of learning of the event using the paper SAE form. The SAE forms should be obtained at [http://prevention.cancer.gov/files/clinical-trials/SAE\\_form.doc](http://prevention.cancer.gov/files/clinical-trials/SAE_form.doc).

11.2.2.3 (B) The written SAE reports will also be emailed to DCP's Regulatory Contractor, CCS Associates at [[contact]](mailto:[contact])

11.2.2.3 (C) The written SAE report will also be emailed to the Consortium Lead Organization PI ([name]), at [[contact]](mailto:[contact]).

It is the responsibility of the CLO to inform the Lead Protocol PI upon receipt of the report from the organization experiencing the event.

11.2.2.4 The DCP Medical Monitor and CCSA regulatory and safety staff will determine which SAEs require FDA submission.

11.2.2.5 The Lead Organization and all Participating Organizations will comply with applicable regulatory requirements related to reporting SAEs to the IRB/IEC.

